3.3.4 Treatment dosing and schedule

3.3.4.1 Phase 1 dosing and dose escalation

During the phase 1 portion, cohorts of patients will be enrolled according to a standard 3 + 3 dose escalation scheme.

Part A

To establish a baseline pharmacokinetic profile for BKM120, phase 1 patients will receive a single dose of BKM120 7 days prior to the initiation of continuous therapy (cycle 0, day -7). PK sampling is described in section 3.4.6. Starting on cycle 1, day 1, patients will receive continuous therapy with vemurafenib and BKM120 during the DLT period (cycle 1 day 1 through cycle 1 day 28) unless dose limiting toxicities occur. Doses will be escalated (see *Table*

5) once the patients receiving the highest current dose have been observed for at least 4 weeks of combination therapy and if DLTs (see *Table 6*) have not been reported in any of 3 patients in a dose level cohort. If 1 of 3 patients experiences a DLT, the cohort will be expanded to six patients and doses will be escalated if no more than 1 of 6 patients in the expanded cohort experiences a DLT. If 2 or more patients in a dose level cohort experience a DLT, then the dose level will be defined as the non-tolerated dose (NTD). Any dose reduction required during the DLT period will be considered a DLT.

The maximum tolerated dose (MTD) for *Part A* will be defined as one dose level below the NTD or BKM120 100 mg PO daily with vemurafenib 960 mg PO bid if this level is achieved without meeting the NTD definition. RP2D will be determined based on the MTD, post-DLT period toxicity, and pharmacokinetic data. There will be no intra-patient dose escalation allowed during the study. For any dose cohort, if a patient is removed from study for reasons that are clearly not treatment-related, then an additional patient will be accrued to that dose level.

Part B

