Patients must not take BRAF therapy for 2 weeks or 5 half-lives of the BRAF inhibitor prior to initiating combination therapy on trial (whichever is shorter). Starting on cycle 1, day 1, patients will receive continuous therapy with vemurafenib and BKM120 during the DLT period (cycle 1 day 1 through cycle 1 day 28) unless dose limiting toxicities occur. PK sampling is described in section 3.4.6. Doses will be escalated (see *Table 5*) once the patients receiving the highest current dose have been observed for at least 4 weeks of combination therapy and if DLTs (see *Table 6*) have not been reported in any of 3 patients in a dose level cohort. If 1 of 3 patients experiences a DLT, the cohort will be expanded to six patients and doses will be escalated if no more than 1 of 6 patients in the expanded cohort experiences a DLT. If 2 or more patients in a dose level cohort experience a DLT, then the dose level will be defined as the non-tolerated dose (NTD).

The maximum tolerated dose (MTD) for *Part B* will be defined as one dose level below the NTD or BKM120 100 mg PO daily with vemurafenib 960 mg PO bid if this level is achieved without meeting the NTD definition. RP2D will be determined based on the MTD, post-DLT period toxicity, and pharmacokinetic data. There will be no intra-patient dose escalation allowed during the study. For any dose cohort, if a patient is removed from study for reasons that are clearly not treatment-related, then an additional patient will be accrued to that dose level. If the maximum tolerated dose has been identified and fewer than 15 patients have been enrolled in Phase 1, *Part B*, additional patients may be enrolled at the MTD or RP2D at the discretion of the principal investigator to a maximum of 15 patients.

Table 5. Phase 1 dose levels

Dose Level	BKM120 Dose	Vemurafenib Dose
-1	60 mg daily	480 mg bid
1	60 mg daily	720 mg bid
2	80 mg daily	720 mg bid
3	100 mg daily	720 mg bid
4	100 mg daily	960 mg bid

Table 6 – Criteria for defining dose-limiting toxicities

TOXICITY	ANY OF THE FOLLOWING CRITERIA
Hematologic^a	≥ CTCAE grade 3 neutropenia for > 7 consecutive days CTCAE grade 3 thrombocytopenia for > 7 consecutive days CTCAE grade 4 thrombocytopenia Febrile neutropenia (ANC < 1.0 x 10 ⁹ /L, fever ≥ 38.5°C)
Renal	Serum creatinine ≥ 2.0 x ULN to ≤ 3.0 x ULN for > 7 consecutive days > CTCAE grade 3 serum creatinine

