Hepatic^b	Total bilirubin ≥ 2xULN to ≤ 3.0 x ULN for > 7 consecutive days > CTCAE grade 3 total bilirubin CTCAE grade 3 AST or ALT for > 7 consecutive days CTCAE grade 4 AST or ALT ALT or AST rise to ≥3x ULN in combination with a rise in bilirubin to ≥ 2x ULN
Endocrine	Grade 2 hyperglycemia (confirmed with a repeat FPG within 24 hours) that does not resolve to grade 0 within 14 consecutive days (after initiation of glimepiride, metformin or glibenclamide) ≥ Grade 3 hyperglycemia (confirmed with a repeat FPG within 24 hours)
Metabolic/ Laboratory	CTCAE grade 3 asymptomatic amylase and/or lipase, not reversible to ≤ CTCAE grade 2 for > 7 consecutive days CTCAE grade 4 asymptomatic amylase and/or lipase
Pancreatitis	≥ CTCAE grade 2
Cardiac	Cardiac toxicity ≥ CTCAE grade 3 or cardiac event that is symptomatic or requires medical intervention Clinical signs of cardiac disease, such as unstable angina or myocardial infarction, or Troponin ≥ CTCAE grade 3
Neurotoxicity	≥ 1 CTCAE grade level increase
Mood alteration	CTCAE grade 2 mood alteration that does not resolve to ≤ grade 1 within 14 days despite medical treatment (for Anxiety only, if worsened from baseline) ≥ CTCAE grade 3 mood alteration
Dermatologic	Any intolerable phototoxicity or skin toxicity (except SCC of the skin amenable to local excision) ≥ CTCAE grade 3 that does not resolve within 7 days with medical management. Any grade 3 or higher skin toxicity associated with superinfection or limiting self-care ADLs. Secondary squamous cell carcinoma of the skin including but not limited to keratoacanthomas amenable to curative excision or other localized curative therapies are NOT classified as DLTs.
Other adverse events	Grade ≥3 non-hematologic, non-hepatic organ toxicity related to drug regimen, EXCLUDING the following: a. Grade 3 nausea or vomiting that resolves to Grade ≤ 1 within 7 days of appropriate supportive therapy b. Grade 3 diarrhea that resolves to Grade ≤ 1 within 7 days with appropriate supportive therapy c. Grade ≥ 3 fatigue that resolves to Grade ≤ 2 within 7 days d. Grade ≥ 3 hyperuricemia that resolves to Grade ≤ 2 within 7 days e. Grade 3 fever

a ≥ CTCAE grade 3 anemia will not be considered DLT unless judged to be a hemolytic process secondary to study drug. ≥ CTCAE grade 3 lymphopenia will not be considered DLT unless clinically significant.

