b For any grade 3 or 4 hepatic toxicity that does not resolve within 7 days to ≤ grade 1 (or ≤ grade 2 if liver infiltration with tumor present), an abdominal CT scan has to be performed to assess if it is related to disease progression.

A single patient is assumed not to tolerate the dose if he/she experiences at least one DLT.

If a lower grade AE leads to a dose interruption of more than 7 doses of BKM120, this AE will be considered as DLT.

If the 2nd occurrence of an initially non-dose limiting toxicity (e.g., grade 3 AST that resolved to ≤ grade 1 within 7 days at 1st occurrence) leads to a dose reduction within 28 days of the first dose of BKM120, this will be considered a DLT.

Parts A & B

Toxicity will be assessed using the NCI Common Toxicity Criteria for Adverse Events, version 4.0 unless otherwise specified (e.g., hyperglycemia). A dose-limiting toxicity (DLT) is defined as an adverse event or abnormal laboratory value assessed as unrelated to disease, disease progression, inter-current illness, or concomitant medications that occurs < 28 days following Cycle 1 Day 1 of BKM120 and vemurafenib, and meets any of the criteria listed in *Table 6*.

Whenever a patient experiences atoxicity that fulfills the criteria for a DLT (or a potential DLT), treatment will be interrupted (if not otherwise specified) and the toxicity will be followed up as described in *Table 7*. Exceptions are CTCAE grade 2 hyperglycemia, CTCAE grade 2 mood alteration, and squamous cell carcinoma of the skin that is amenable to cure by local excision. Grade 3 skin toxicity (except SCC of the skin amenable to local excision) and grade 3 photosensitivity will only be considered DLTs if they are intolerable and if they do not resolve within 7 days with appropriate medical management. In the case of hyperglycemia and mood alteration, treatment will be continued under appropriate co-medication, and in the case of SCC of the skin, local excision will be performed. The rules for re-initiation and dose modification of BKM120 and vemurafenib treatment are outlined in *Table 8*. Prior to enrolling patients into a higher dose level, \geq CTCAE grade 2 adverse events will be reviewed for all patients at the current dose level.

After the 28-day DLT period, dose modifications will be made as outlined in *Table 8*. Treating physicians must notify the PI immediately of any unexpected \geq CTCAE grade 3 adverse events or laboratory abnormalities.

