5.3 Analysis Plan

All patients who received at least 75% of prescribed cohort dose during the DLT period will be considered evaluable. Patients not evaluable will be replaced.

Phase 1 portion of the study

Safety and tolerability will also be assessed by clinical review of all relevant parameters including adverse experiences (AEs), laboratory tests, and physical exam. Adverse experiences will be summarized as counts and frequencies for each dose level. Other safety endpoints will be summarized as appropriate. These data are descriptive in nature and statistical analysis tools will not be required. The recommended phase 2 dose will be determined using safety data including DLTs and post-DLT toxicity, the dose-response relationship, and PK data.

Pharmacokinetic data will be acquired as described in section 3.4.6 and average values and standard deviations at each time point will be reported.

Phase 2 portion of the study

The PFS duration is defined as the time from the date of start of protocol therapy to the date of the first documented progression or death due to any cause. A patient who has not progressed or died by the date of the analysis cut-off or when the patient received any further anticancer therapy would have the PFS censored at the time of the last adequate tumor assessment before the first of the cut-off date or of the anticancer therapy date. All patients will be followed for 6 months and proportion of patients that are progression free at 6 months will be calculated. We assume that combination treatment will have at least 70% PFS rate versus the undesirable PFS of <50% at 6 months. The phase 2portion is designed based single stage binomial design with the type I alpha of 5% and the power of 80%. If ≥ 23 patients ultimately achieve 6 months PFS, then further investigation of the drug is warranted.

As secondary efficacy endpoints, the median PFSand OS will be estimated using exact binomial distribution; time to progression will be estimated using Kaplan-Meier methods. The 6-month PFS and 95% confidence intervals will be reported. ORR will be reported as frequencies and proportions with exact 95% confidence intervals from the Binomial distribution. The frequencies of individual toxicities thought to be probably, possible, or definitely related to study drug will be reported as well as the incidence of any grade 3, 4, and 5 toxicities regardless of attribution.

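### Section 5.3 replaces every patient below the 75% dose threshold with no exception for a DLT, and no text says how this fits the DLT count in 3.3.4.1

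*Combined protocol and SAP*

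**What the plan says.** Section 5.3 opens, above both its phase 1 and its phase 2 sub-headings, with the rule: "All patients who received at least 75% of prescribed cohort dose during the DLT period will be considered evaluable. Patients not evaluable will be replaced". Dose received is the only test, and a DLT is not mentioned. Section 5.2 gives the same 75% definition without a DLT clause, there attached to the 37 evaluable patients of the phase 2 design.

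Section 3.3.4.1 holds the escalation rules, in the same terms for Parts A and B:

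- The non-tolerated dose is reached "If 2 or more patients in a dose level cohort experience a DLT".
- On patient-level tolerance: "A single patient is assumed not to tolerate the dose if he/she experiences at least one DLT".
- On extra patients: "if a patient is removed from study for reasons that are clearly not treatment-related, then an additional patient will be accrued" to that dose level.
- A missed-dose criterion: "If a lower grade AE leads to a dose interruption of more than 7 doses of BKM120, this AE will be considered as DLT".
- Table 6 defines several DLTs by duration, for example "CTCAE grade 3 thrombocytopenia for > 7 consecutive days".
- When a DLT or potential DLT occurs, treatment is interrupted unless the protocol provides otherwise. The named exceptions are grade 2 hyperglycemia, grade 2 mood alteration and locally excisable skin squamous cell carcinoma.

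Sections 3.1 and 5.1 both refer the reader to section 3.3.2.1 for dose escalation. There is no such section; the content is in 3.3.4.1.

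**The concern.** A DLT usually interrupts dosing, so the toxicity that the 3+3 rule counts also lowers the dose that decides evaluability under 5.3. Read literally, 5.3 then orders that patient replaced, while 3.3.4.1 counts patients with a DLT and provides for an added patient when removal is clearly unrelated to treatment.

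Take a cohort of three in which two patients each have an adverse event that interrupts more than 7 BKM120 doses in Cycle 1. Under 3.3.4.1 the level is non-tolerated. Under 5.3 both patients are below 75% of BKM120 and are replaced. If their DLTs left the count with them, and the third patient and both replacements had none, the cohort would read 0 of 3 and escalation would proceed. Even if the DLTs stay in the count, the plan does not say whether the cohort is then 3 or 5 patients, and the rule is written for 3 and 6.

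At stake is the maximum tolerated dose, a main input to the recommended phase 2 dose. An error of this kind would run toward too high a dose.

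**Working it through.** **The plan's own figure.** Section 5.2 estimates at most 24 phase 1 patients. Four predefined dose levels × 6 patients = 24. This reproduces it, with no allowance for replacements of any kind, so it does not settle which rule was meant to govern.

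**Overlap of the two rules.** Inputs: a DLT period of 28 days (3.1); BKM120 once daily and vemurafenib twice daily (3.3.3), hence 28 and 56 scheduled doses, 84 in all; threshold 75% (5.3).

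- 7 BKM120 doses missed: 21/28 = 75.0%, evaluable.
- 8 missed, the fewest that meet the missed-dose DLT criterion: 20/28 = 71.4%, not evaluable on BKM120. Every patient who meets that criterion within Cycle 1 is therefore below 75% of BKM120.
- A DLT that ends BKM120 dosing for the cycle with the last dose on day 20 or earlier: at most 20/28 = 71.4%.
- Both drugs held on 8 days of Cycle 1, as can happen with a DLT defined by more than 7 days of toxicity: BKM120 20/28 = 71.4%, vemurafenib 40/56 = 71.4%, combined 60/84 = 71.4%. This patient fails however the 75% is calculated.

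Not every DLT patient falls below 75%. A late DLT, or one managed without a long interruption, can stay above it. Where only one drug is interrupted, the answer depends on whether the 75% applies to each drug or to both together, which 5.3 does not say.

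**Size, if the DLTs of replaced patients were lost.** Let *p* be the true DLT rate and *f* the share of DLT patients replaced and lost from the count. The documents give neither, so both are assumed. If all DLT-free patients stay evaluable, the DLT rate among those counted is

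q = p(1 − f)/(1 − pf).

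Under the rule in 3.3.4.1, a level clears with 0 of 3, or with 1 of 3 followed by 0 of the next 3:

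P(clear) = (1 − q)³ + 3q(1 − q)² × (1 − q)³.

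For p = 0.33:

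- f = 0: q = 0.330; P = 0.301 + 0.444 × 0.301 = 0.434.
- f = 0.10: q = 0.297/0.967 = 0.307; P = 0.333 + 0.442 × 0.333 = 0.480.
- f = 0.25: q = 0.2475/0.9175 = 0.270; P = 0.389 + 0.432 × 0.389 = 0.557.

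| Assumed p | f = 0 | f = 0.10 | f = 0.25 |
|---|---|---|---|
| 0.25 | 60% | 64% | 71% |
| 0.33 | 43% | 48% | 56% |
| 0.40 | 31% | 35% | 43% |

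The f = 0 column is the rule with every DLT counted.

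**Sensitivity.** If a share g of DLT-free patients is also lost, q = p(1 − f)/[p(1 − f) + (1 − p)(1 − g)]. At g = f this returns q = p and the effect vanishes. The table therefore depends on DLT patients being lost more often than others.

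**The case against.** The strongest reply is that replacing a patient does not erase that patient's DLT. The stopping rule in 3.3.4.1 counts patients in the cohort who experience a DLT and never uses the word evaluable. Section 5.2 ties the 75% test to the phase 2 patients, which suggests an efficacy set. The recommended-dose sentence in 5.3 names DLTs as an input. Adverse events of grade 2 or higher are reviewed before escalation (3.3.4.1), and the monitoring committee chair must authorise escalation from a report that includes any DLT (Appendix 6.1). The thresholds can even be read together: 7 missed BKM120 doses is exactly 75%, and more than 7 missed for an adverse event is a DLT.

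Much of this stands, and it limits the point in three ways:

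- A reader might infer that the plan discards these DLTs and so sets the maximum tolerated dose too high. Nothing in 5.3 says that they leave the count.
- A reader might infer that 3.3.4.1 forbids any other added patient, or expressly counts DLTs at any dose received. It says neither, and for Part B it allows further enrolment to a maximum of 15 once the maximum tolerated dose is known.
- A reader might build a case on grade 4 hyperglycemia, where Table 8 stops BKM120 but lets vemurafenib continue. Sections 3.3.4.1 and 3.3.5 leave unclear whether Table 8 applies inside the phase 1 DLT period, so that case is not used here.

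What the reply does not meet is the text of 5.3. The sentence stands above both phase headings, speaks of the cohort dose and the DLT period, and orders replacement, which is an enrolment action. No text confines it to phase 2 or makes it yield to 3.3.4.1.

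**Conclusion.** The point holds as a gap between two rules that should be closed; it is not a demonstrated bias. Section 5.3 replaces all patients below 75% without a DLT exception. Section 3.3.4.1 counts patients with a DLT and gives no basis for replacing them on that account. At least one DLT defined in the protocol puts the patient at 71.4% of BKM120 or less whenever it is met within Cycle 1.

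If every DLT is counted, as the surrounding text favours, the chance of clearing a level is not inflated. If 5.3 were applied literally and those DLTs were lost, a level with a true DLT rate of 33% would clear 48% or 56% of the time instead of 43%. That rests on the assumed rate, an assumed 10% or 25% of DLT patients lost, and all DLT-free patients staying evaluable. The finding itself rests on the wording and the dose arithmetic, not on those probabilities. It should be fixed because it bears on cohort decisions and the remedy is small.

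**What to change.** Add to 5.3:

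> For phase 1 dose-escalation decisions only, a patient with a DLT after at least one dose of combination therapy is counted in the cohort as in section 3.3.4.1, whatever dose was received, and is not replaced; for these decisions the 75% rule applies only to patients without a DLT. This does not alter the phase 2 analysis set.

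Also state whether the 75% applies to each drug or to both combined, and correct the pointer to 3.3.2.1 in sections 3.1 and 5.1 to 3.3.4.1.

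The limit to escalation decisions matters because phase 1 patients treated at the recommended dose enter the 37 of phase 2 (5.2). The effect of the 75% rule on the 6-month PFS denominator is a separate question, which this wording leaves untouched.

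The cost is a few sentences and two corrected cross-references. The downside is that escalation may stop one level earlier than under a literal reading of 5.3.

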5.2. Sample Size/Accrual Rate

This study will use the standard 3+3 dose escalation design to determine the RP2D of BKM120 in combination with vemurafenib (phase 1) followed by a single-stage binomial phase 2 design of 37 evaluable patients (any patient receiving at least 75% of prescribed cohort dose during the DLT period) to determine the PFS rate at 6 months.

For the Phase 1 portion

A Phase 1 dose escalation design using the standard 3+3 scheme will be followed and the sample size is not predetermined. We estimate the phase 1 portion of this trial will require a minimum of 2 patients from four predefined dose levels (see *Table 5*) to determine the phase 2 dose (MTD). The estimated maximum number of patients is 24. The final sample size of the study depends primarily on clinical considerations rather than on statistical considerations.

For the Phase 2 portion

The sample size for the phase 2 portion of this study is determined using single-stage binomial design for phase 2 studies. Preliminary data from trials of vemurafenibmonotherapy in advanced melanoma suggest a median PFS of approximately 6 months^{4,5,17}. The proposed design will be used to test the null hypothesis that the 6 month PFS rate of the study combination is 50% or less (which would not be clinically desirable) versus the alternative hypothesis that the true 6 month PFS rate is greater 70%, which would be considered clinically meaningful. The maximum total sample size will be 37 in Phase 2 including patients in the phase 1 portion of the study treated at the RP2D.

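### The phase 2 go rule of at least 23 of 37 has a type I error of 9.4%, not the stated 5%; with 37 patients the cut-off must be 24

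*Combined protocol and SAP*

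**What the plan says.** Section 5.2 describes a "single-stage binomial phase 2 design of 37 evaluable patients". The aim is to "test the null hypothesis that the 6 month PFS rate of the study combination is 50% or less", against the "alternative hypothesis that the true 6 month PFS rate is greater 70%, which would be considered clinically meaningful". It adds: "The maximum total sample size will be 37 in Phase 2", a figure that includes phase 1 patients treated at the recommended phase 2 dose. Section 3.3.4.3 also gives 37.

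Section 5.3 repeats the two rates ("We assume that combination treatment will have at least 70% PFS rate versus the undesirable PFS of <50% at 6 months") and gives the error rates as a "single stage binomial design with the type I alpha of 5% and the power of 80" (per cent). It also says: "Patients not evaluable will be replaced". The decision rule follows: "If ≥ 23 patients ultimately achieve 6 months PFS, then further investigation of the drug is warranted". No other cut-off, error rate or interim look appears anywhere in the document.

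**The concern.** In a single-stage binomial design, the sample size, null rate and cut-off together fix the type I error. The alternative rate then fixes the power. All of these are given, so the stated 5% and 80% can be checked directly, and a cut-off of 23 does not deliver them.

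Phase 2 has no control arm, so this cut-off is the main statistical protection against taking an inactive combination forward. If it is one patient too low, a combination with a true 6-month PFS rate of 50% is called worth pursuing more often than the plan admits. A result of exactly 23 of 37 would be declared positive although the 5% test does not reject the null.

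**Working it through.** **Inputs**

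| Input | Value | Source |
|---|---|---|
| Evaluable patients, n | 37 | 5.2; 3.3.4.3 |
| Null rate, p0 | 0.50 | 5.2, 5.3 |
| Alternative rate, p1 | 0.70 | 5.2, 5.3 |
| Type I error | 5% | 5.3 |
| Power | 80% | 5.3 |
| Go rule | r = 23 or more | 5.3 |

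Sidedness is not stated. I take the test as one-sided because the null is directional and the rule uses only the upper tail.

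**Step 1. Reproduce n = 37.** The one-sided normal approximation is

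n = [(z₀.₉₅ √(p0(1−p0)) + z₀.₈₀ √(p1(1−p1))) / (p1−p0)]²
= [(1.645 × 0.5 + 0.842 × 0.458) / 0.20]² = 36.5, rounded up to 37.

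An exact search agrees. For n from 20 to 59, taking the lowest cut-off that keeps the type I error at or below 5%, the smallest n with power of at least 80% is 37. Its cut-off is 24.

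**Step 2. Exact operating characteristics at n = 37.** With X binomial(37, p), the type I error is P(X ≥ r | p = 0.50) and the power is P(X ≥ r | p = 0.70), where

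P(X ≥ r | p) = Σₖ₌ᵣ³⁷ C(37, k) pᵏ (1−p)³⁷⁻ᵏ.

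| Go if at least | Type I error | Power at 70% |
|---|---|---|
| 22 | 0.1620 | 0.9396 |
| **23 (as written)** | **0.0939** | **0.8870** |
| **24** | **0.0494** | **0.8071** |
| 25 | 0.0235 | 0.6983 |

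The written rule gives 9.4% and 88.7%. Of these cut-offs only 24 meets both targets.

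**Step 3. Could another reading give 23?**

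- *Normal approximation for the cut-off.* The mean under the null is 37 × 0.5 = 18.5 and the SD is √(37 × 0.25) = 3.041. The 5% critical value is 18.5 + 1.645 × 3.041 = 23.50, so the count must again reach 24. The approximate type I error of 23 or more is 6.9% without continuity correction and 9.4% with it.
- *Two-sided 5%.* This is stricter, so it cannot support a lower cut-off.
- *A different denominator with r = 23.* At n = 35 the type I error is 4.5% but power is 77.3%; at n = 36 power is 83.7% but the type I error is 6.6%. With r fixed, both rise with n, so no n meets both targets.
- *A lower null rate.* At n = 37, a cut-off of 23 gives 4.6% at a null of 47% and 5.9% at 48%. It holds 5% only if the null is about 47% or lower; the plan says 50%.

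**Step 4. What a result at the boundary would mean.** The exact (Clopper–Pearson) 90% interval is the one that corresponds to a one-sided 5% test.

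| Result | Rate | One-sided exact p | Exact 90% interval |
|---|---|---|---|
| 23/37 | 62.2% | 0.094 | 47.3% to 75.5% |
| 24/37 | 64.9% | 0.049 | 50.05% to 77.8% |

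The interval for 23/37 includes the 50% null. The interval for 24/37 just excludes it.

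**The case against.** The strongest reply concerns consequence. This is a phase 2 screening rule that leads only to further study, and a sponsor may reasonably accept about 10% type I error at that stage. The two cut-offs lead to different decisions only if exactly 23 of 37 patients succeed, which has probability 0.0939 − 0.0494 = 4.4% at a true rate of 50% and 0.8870 − 0.8071 = 8.0% at 70%. That is fair on impact, but the plan does not choose 10%. It states 5%, and the rule contradicts it.

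Three further points limit the wording but not the conclusion:

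- One-sidedness is inferred. The only natural alternative, a two-sided 5% test, makes 23 look worse.
- Section 5.3 promises 95% intervals for 6-month PFS. The exact 95% intervals are 44.8% to 77.5% for 23/37 and 47.5% to 79.8% for 24/37, and both include 50%. The reported interval will therefore not separate the two cut-offs. This is because a 95% interval matches a one-sided 2.5% test; the tail probabilities carry the argument.
- The go rule does not repeat the denominator, and section 5.2 calls 37 a maximum. But the design is defined on 37 evaluable patients and non-evaluable patients are replaced, so a smaller planned denominator does not explain 23.

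**Conclusion.** The concern holds. For the plan's own inputs, the rule of at least 23 of 37 has an exact one-sided type I error of 9.4%, which is 0.0939/0.05 = 1.9 times the stated rate, and power of 88.7% rather than 80%. The sample size of 37 is correct, and its matching cut-off is 24 (4.9% and 80.7%). The figures would fit if more than 23 had been meant, but the document does not say so and the conclusion does not depend on it.

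The calculation assumes that 6-month status is known for all 37 patients. Section 5.3 censors PFS at the start of other anticancer therapy but does not say how such patients count in the 6-month proportion. Counting them as failures would lower both type I error and power; excluding them would change the denominator, and 24 would no longer be the matching cut-off.

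**What to change.** In section 5.3, change the go rule to at least 24 of 37 evaluable patients progression-free at 6 months. State that the test is exact and one-sided, with a type I error of 0.049 at a 50% rate and power of 0.807 at 70%. Add that these figures assume a known 6-month status for all 37, and say how patients censored before 6 months count.

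If the sponsor wants to keep 23, restate both operating characteristics: type I error 9.4% and power 88.7%.

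The cost is one number and a sentence or two. No extra patients are needed and the 80% power target is still met. Make the change before any phase 2 outcomes are known, because a cut-off moved afterwards is not credible.
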